1.0 Overview

1.1 Background and Justification for Missing at Random (MAR) Assumption

The COVID-19 pandemic is interfering with the conduct of many ongoing trials, with potential impacts on treatment duration and the collection, analysis and the interpretation of clinical trial data. Some protocol-specified visits in the clinical trials may be impacted due to COVID-19 infection or logistical restrictions during the pandemic. For example, some scheduled visits may be missed due to self-quarantine or local government restrictions on travel; some visits may also be delayed or canceled due to healthcare resource constraints during the pandemic. Impacted visits due to COVID-19 will be recorded in the database. The probability of having missed visits and missing data due to COVID-19 infection or logistical restrictions related to the COVID-19 pandemic can be reasonably assumed to be unrelated to the unobserved values. Therefore, for the purpose of statistical analysis, it is reasonable to assume that these missing data are missing at random (MAR) and the statistical models that require MAR assumption are appropriate. In some cases, sensitivity analyses may be performed to assess the impact of missing data and the robustness of the conclusion.

1.2 FDA Guidance

FDA provided two guidance documents^{1,2} in March 2020 and June 2020 on the efficacy collection and possible changes in the statistical analysis plan:

- "With respect to efficacy assessments, FDA recommends consultation with the appropriate review division regarding protocol modifications for the collection of efficacy endpoints, such as use of virtual assessments, delays in assessments, and alternative collection of research-specific specimens, if feasible. For individual instances where efficacy endpoints are not collected, the reasons for failing to obtain the efficacy assessment should be documented (e.g.,

identifying the specific limitation imposed by COVID-19 leading to the inability to perform the protocol-specified assessment)."

- "If changes in the protocol will lead to amending data management and/or statistical analysis plans, the sponsor should consider doing so in consultation with the applicable FDA review division. Prior to locking the database, sponsors should address in the statistical analysis plan how protocol deviations related to COVID-19 will be handled for the prespecified analyses."

1.3 EMA Guidance

EMA provided guidance³ in March 2020:

- "At this point in time it is not possible to give general applicable advice on how the different aspects related to the pandemic should be handled, as implications on clinical trials are expected to be manifold. Impact on the data collection, analysis and interpretation of results for each trial will need a thorough case-by-case assessment."
- "As a general principle, there are strong scientific reasons to conduct trials as planned and implement changes only when there is a convincing scientific reason that it improves interpretability of results."

1.4 Missing Data Handling for Missing Due to COVID-19 for Dichotomized Variables

In this document, a missing data handling method is proposed to handle missing data due to COVID-19 infection or logistical restrictions related to the COVID-19 pandemic under the general MAR framework. In particular, we explain using multiple imputation (MI) to handle missing data due to COVID-19 in dichotomized variables in conjunction with non-responder imputation (NRI) for missing data due to other reasons.

2.0 Non-responder Imputation Incorporating Multiple Imputation (NRI-MI)

2.1 Overall Description of the Method

For a dichotomized outcome variable with missing data, the NRI-MI will categorize any subject who does not have evaluation during a pre-specified visit window as a non-responder for the visit, with two exceptions:

- If the subject is a responder both before and after the pre-specified visit window in the specific Study Period, the subject will be categorized as a responder for the visit.
- If the reason for missing (e.g., missed visits, incomplete visit, out-of-schedule visits, or discontinuations of study drug) is due to COVID-19, the information will be captured in the database and the subject's response status will be imputed using multiple imputation.

Subjects whose change/percent change from Baseline cannot be calculated because of a missing Baseline will be considered as a non-responder at all post-baseline visits unless the post-baseline value is zero.

Non-responder imputation incorporating multiple imputation (NRI-MI) for missing due to COVID-19 will be implemented as follows.

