### Interruption/Discontinuation of Study Drug Due to COVID-19 Infection

During the study drug dosing period, a subject with confirmed (viral test positive) or suspected COVID-19 infection can only be dosed with study drug if the following COVID-19 viral clearance criteria are met:

- At least 14 days since first positive test result have passed in asymptomatic patients or at least 14 days since recovery, defined as resolution of fever without use of antipyretics and improvement in symptoms.

Delays in study drug dosing due to the above COVID-19 testing guidance for subjects must be discussed with the AbbVie medical contact, along with the possibility of premature discontinuation from the study drug dosing period. Follow subsequent protocol Section 5.6 for subjects who discontinued study drug.

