## APPENDIX D. ACTIVITY SCHEDULE

The following table shows the required activities across the subject encounters. The individual activities are described in detail in the **Operations Manual**. Allowed modifications due to COVID-19 and/or the geo-political conflict in Ukraine and surrounding impacted regions are detailed within the Operations Manual.

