9.2 Handling of Missing Data

Missing data could occur due to various reasons, including missing visits/assessments, early withdrawal from the study, or missing due to COVID-19 infection or logistic restriction.

The COVID-19 pandemic is interfering with the conduct of many ongoing trials, with potential impacts on treatment duration and the collection, analysis and the interpretation of clinical trial data. Some protocol-specified visits in the clinical trials may be impacted due to COVID-19 infection or logistical restrictions during the pandemic. For example, some scheduled visits may be missed due to self-quarantine or local government restrictions on travel; some visits may also be delayed or canceled due to healthcare resource constraints during the pandemic. Impacted visits due to COVID-19 will be recorded in the database. The probability of having missed visits and missing data due to COVID-19 infection or logistical restrictions related to the COVID-19 pandemic can be reasonably assumed to be unrelated to the unobserved values. Therefore, for the purpose of statistical analysis, it is reasonable to assume that these missing data are missing at random (MAR) and the statistical models that require MAR assumption are appropriate. Sensitivity analyses will be performed to assess the impact of missing data and the robustness of the conclusion.

Handling of missing data for the efficacy analyses is described below.

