9.2.1 Categorical Endpoints

Non-Responder Imputation incorporating multiple imputation to handle missing data due to COVID-19 (NRI-MI) will be the approach for handling missing data in the analysis of categorical endpoints among all ITT Populations except for the ITT_Res Population. The NRI-MI will categorize any subject who does not have an evaluation during a pre-specified visit window as a non-responder for the visit. The only exceptions are: 1) when the subject is a responder both before and after the visit window in the particular Study Period, the subject will be categorized as a responder for the visit; 2) missing data due to COVID-19 infection or logistical restriction will be handled by MI. Subjects who receive alternative PsO treatment regardless of premature discontinuation of study drug or receive RZB as the rescue medication will be counted as non-responders at later visits. Subjects whose change/percent change from Baseline cannot be calculated because of a missing Baseline will be considered as a non-responder at all post-baseline visits, unless the post-baseline value is zero. More details are provided in [Appendix D](#).

Of note, during the Primary Analysis for Period A upon completion of Week 16, the NRI-MI analysis will only be performed at all visits up to Week 16.

Observed Cases (OC) will be the approach for handling missing data in the analysis of categorical endpoints among the ITT_Res Population. The OC analysis will not impute values for missing evaluations, and thus a subject who does not have an evaluation on a scheduled visit will be excluded from the OC analysis for that visit. OC will exclude values after a subject receive alternative PsO treatment regardless of premature discontinuation of study drug.

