2.3 Imputation Algorithm

It is reasonable to assume the missing values of the longitudinal data for an outcome variable (e.g., PASI, the original scale of PASI 90, at each post-baseline visit) follows a monotone missing pattern. In practice, the missing data of the outcome variable might have an arbitrary (non-monotone) missing data pattern. An extra step may be added accordingly, to augment data into a monotone missing pattern.

For the outcome variable (e.g., PASI at each visit), K 'complete' datasets can be generated in two steps: augmentation step and imputation step. K, the number of repetitions, is determined below.

Augmentation Step

For datasets with non-monotone missing data pattern, the augmentation step will first impute enough values to augment the data into a monotonic missing pattern:

Markov Chain Monte Carlo (MCMC) will be applied to augment the data using PROC MI with the MCMC IMPUTE=monotone statement, assuming a multivariate normal distribution. The augmented data will be used in the subsequent imputation step to generate 'complete' datasets.

- For analyses for the ITT_A Population: Covariates included in the model are treatment group, Baseline body weight as a continuous variable, prior exposure to any systemic and/or biologic treatment for PsO (0, \geq 1), Baseline and all post-baseline visits of the outcome variable up to the end of Period A.
- For analyses for the ITT_B_Combined, ITT_B_NR and ITT_B_R Populations: Covariates included in the model are treatment group, PASI score at Baseline and at the Entry of Period B, and the outcome variable collected at the Entry of Period B and all later visits.

- For analyses for the ITT_LT Population: Covariates included in the model are treatment group, Baseline body weight as a continuous variable, prior exposure to any systemic and/or biologic treatment for PsO ($0, \geq 1$), PASI score at Baseline and at the Entry of Period B, and the outcome variable collected at the Entry of Period B and all later visits. Subjects randomized to RZB at Baseline and did not enter Period B will be included in the analysis and will be counted as non-responders. To accommodate the 1:1 re-randomization, half (round down to integer) of the subjects randomized to APR at Baseline and did not enter Period B will be included in the analysis and will be counted as non-responders.

Of note, categorical variables are included using the form of dummy variables.

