2.4 Derivation of Response Status and Non-Responder Imputation

For each 'complete' dataset, the imputed post-baseline values will be rounded to the same precision as the observed data. Response status (e.g., PASI 90 at each visit) will be determined accordingly.

The imputed response status for missing due to reasons other than COVID-19 will be overridden by non-responder imputation (Section 2.1) to ensure that multiple imputation is only applied to missing due to COVID-19:

- Using NRI approach, all missing due to reasons other than COVID-19 will be categorized as non-responders. In addition, subjects whose change/percent

change from Baseline cannot be calculated because of a missing Baseline will be considered as a non-responder at all post-baseline visits, unless the post-baseline value is zero.

- The only exception is that a subject will be categorized as a responder for the visit if the subject is a responder both before and after an SAP-specified visit window in the particular Study Period.

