/*****
*/

/*FOR MI, SKIP THE FOLLOWING CODE, PROCEED TO THE CODE AFTER ANALYSIS
MODEL *//*OVERRIDE MISSING VALUES NOT DUE TO COVID-19 WITH TRADITIONAL
NRI*/
DATA ALLF; SET ALL;
  /*COVID19_XX='Y' IF MISSING AT WEEK XX IS DUE TO COVID-19; IF NOT,
OVERRIDE WITH TRADITIONAL NRI*/
  /*VARIABLE PASI90 NRI XX: TRADITIONAL NRI DATA AT WEEK XX, WHICH
COVERS THE SPECIAL HANDLING SUCH AS THE BEFORE-AND-AFTER EXCEPTION IN
THE PARTICULAR STUDY PERIOD*/
  IF COVID19_16 NE 'Y' THEN PASI90_16= PASI90NRI_16;
RUN;
PROC SORT DATA=ALLF; BY _IMPUTATION_ SUBJID; RUN;

/*****
/*ANALYSIS MODEL*/
/*****
```

```
/*KEY CODE: ANALYZING EACH 'COMPLETE' DATASET*/  
/*****  
/*INDIVIDUAL-LEVEL DATA --> # OF RESPONDERS & # OF SUBJECTS, TO BE READ-  
IN TO PROC STD RATE*/  
PROC FREQ DATA=ALL;  
  BY IMPUTATION ;  
  TABLES TRT01PN*STRATAN* PASI90 16/LIST NOCUM NOPRINT OUT=COUNT_TABLE;  
  /*WEEK 16 RESULTS AS AN EXAMPLE*/  
RUN;  
DATA COUNT_TABLE; SET COUNT_TABLE;  
  DROP PERCENT;  
RUN;  
PROC TRANSPOSE DATA=COUNT_TABLE OUT=FREQ_TABLE PREFIX=RESP;  
ID PASI90_16;  
BY IMPUTATION_ TRT01PN STRATAN;  
VAR COUNT;  
RUN;  
DATA FREQ_TABLE1; SET FREQ_TABLE;  
  CASE=RESP1;  
  SIZE=SUM(RESP0, RESP1);  
  KEEP _IMPUTATION_ TRT01PN STRATAN CASE SIZE;  
RUN;  
  
/*RE-ORDER TO SET 1 (PLACEBO) AS THE REFERENCE GROUP*/  
DATA FREQ_TABLE2; SET FREQ_TABLE1;  
  IF TRT01PN=2 THEN TRT01PN=0;  
RUN;  
  
/*CALCULATE THE COMMON RISK DIFF FOR EACH COMPLETE DATASET*/  
PROC STD RATE DATA=FREQ_TABLE2  
  METHOD=MH STAT=RISK EFFECT=DIFF;  
  BY _IMPUTATION_;  
  POPULATION GROUP=TRT01PN EVENT=CASE TOTAL=SIZE;  
  STRATA STRATAN / ORDER=DATA STATS(CL=NONE) EFFECT;  
  ODS OUTPUT EFFECT=EFFECT;  
RUN;  
  
/*COMBINING RESULTS USING PROC MIANALYZE*/  
/*****  
PROC MIANALYZE DATA=EFFECT;  
  ODS OUTPUT PARAMETERESTIMATES=RISK_DIFF_MH;  
  MODELEFFECTS RiskDiff;  
  STDERR StdErr;  
RUN;
```

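### In Period B, subjects who stop drug because of COVID-19 and have no Week 52 assessment are imputed close to on-drug response, while other such stoppers count as non-responders

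*SAP*

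**What the plan says.** SAP Appendix D 2.1 makes two exceptions to non-responder imputation (NRI). One covers subjects who respond on both sides of a gap. The other covers missing data whose cause, in the SAP's own list, reads "missed visits, incomplete visit, out-of-schedule visits, or discontinuations of study drug) is due to COVID-19". These go to MI. For the rest, Appendix D 2.4 states: "Using NRI approach, all missing due to reasons other than COVID-19 will be categorized as non-responders". The sample code makes the choice with one flag per visit: "IF COVID19_16 NE 'Y' THEN PASI90_16= PASI90NRI_16".

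The justification is in SAP 9.2 and Appendix D 1.1: the chance of COVID-19 missingness "can be reasonably assumed to be unrelated to the unobserved values". The examples given there are quarantine, travel limits, and visits delayed or cancelled.

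For the re-randomized populations, Appendix D 2.3 specifies: "Covariates included in the model are treatment group, PASI score at Baseline and at the Entry of Period B", plus the outcome from entry to Period B onwards.

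The protocol foresees stopping for this reason. Its section on COVID-19 infection during dosing (within 5.5) says that dosing delays must be discussed with the sponsor's medical contact, "along with the possibility of premature discontinuation from the study drug dosing period".

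The Period B estimands (Protocol 3.1, SAP 2.1) count the Week 52 outcome whether or not study drug was stopped early. Rescue and alternative psoriasis treatment count as failure. SAP 9.3.3 and 9.4.3 plan no sensitivity analysis for the primary or ranked endpoints, although SAP 9.2 says such analyses will be done.

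**The concern.** A missed visit in a subject still on treatment can reasonably be treated as unrelated to the unseen PASI. Permanently stopping the assigned drug is different, because it plausibly changes the PASI that would have been seen. The SAP's argument does not discuss that case, yet its rule includes it.

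With only arm and PASI history in the model, a stopper's later values are drawn from subjects in the same arm who are mostly still treated. That estimates what would have happened had the subject continued, which the estimand does not ask. A subject who stops for any other infection and leaves is a non-responder. Two people with the same treatment history and the same gap are thus handled differently because of the recorded cause alone. The analyses affected are the Period B primary endpoint and the two ranked secondary endpoints, and no planned analysis would show how much the choice matters.

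**Working it through.** **1. Plan's own figure (SAP 2.4; Protocol 7.8).** Inputs: 50% vs 20%, 60 per group, two-sided 0.05, chi-square with pooled variance under the null.
- Null SE = √(2 × 0.35 × 0.65 / 60) = 0.0871. Alternative SE = √((0.25 + 0.16) / 60) = 0.0827.
- z = (0.30 − 1.96 × 0.0871) / 0.0827 = 1.56, so power is 94.1%. The stated figure of more than 90% is reproduced.

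**2. What the imputation model does with a stopper.** A small simulation imputed Week 52 by regression on arm, entry value and Week 28 value, using percent improvement with a cut at 90. Assumed, not from the documents: 6 of 60 APR/RZB subjects stop after Week 28, have no later visits, and lose 40 points of improvement off drug. Stoppers were imputed at 49.9% response. The observed on-drug rate was 49.9%, and the off-drug rate built into the simulation was 3.3%. The 3.3% only reflects the assumed loss. The informative result is that imputed and on-drug rates coincide when no off-drug data enter the model.

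**3. Shift between MI and NRI.** The documents give no number of stoppers, so k is assumed. If imputed response equals the arm's planning rate, and NRI would give zero:
- k in each arm: k × (0.50 − 0.20) / 60. For k = 1 this is 0.5 point; for k = 3 it is 1.5 points.
- Three in APR/RZB only: 3 × 0.50 / 60 = 2.5 points towards risankizumab.
- Three in APR/APR only: 3 × 0.20 / 60 = 1.0 point towards apremilast.

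**4. Power if these subjects were non-responders.** With a share f of an arm affected, its rate becomes p(1 − f).

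| f | Both arms: difference, power | APR/RZB only: difference, power |
|---|---|---|
| 0% | 30.0, 94.1% | 30.0, 94.1% |
| 2% | 29.4, 93.4% | 29.0, 92.7% |
| 5% | 28.5, 92.2% | 27.5, 90.0% |
| 10% | 27.0, 89.9% | 25.0, 84.1% |

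**5. Does the other exception help?** It applies "when the subject is a responder both before and after the visit window in the particular Study Period". Week 52 is the last efficacy visit of Period B, so nothing follows it and the exception cannot act there.

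**6. Does the same problem arise in Period A?** Risankizumab is given at Baseline and Week 4 only. SAP 6.0 credits 84 days of treatment after the last dose, and Week 4 plus 84 days is Week 16. A risankizumab subject has no dose left to stop after Week 4, whereas apremilast continues until the day before Week 16.

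**The case against.** Several counter-arguments stand and limit the point.

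- **Few subjects are affected.** Protocol 5.6 asks stoppers to keep attending, and observed values are used. Those who meet rescue criteria, or who receive rescue or alternative treatment, are already non-responders. Only a stopper with a missing assessment reaches MI.
- **The imputation is close to on-drug, not exactly so.** Off-drug values from stoppers who stay in the study also inform the arm's model, as does the subject's own history.
- **NRI does not deliver the estimand either.** It is simply the SAP's rule for every other stopper. This argues for consistency and does not show that NRI is unbiased.
- **The missing-at-random text is not confined to visits.** It mentions effects on treatment duration and covers missing data due to infection. Even so, it offers no argument about unseen PASI after drug is stopped.

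A reader might infer that the co-primary results in Period A are also tilted towards risankizumab. The dosing schedule does not support that. A condition on being on drug at Week 16 would fall mainly on apremilast subjects and would itself favour risankizumab.

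A reader might also infer that conflict-related missed visits are wrongly set to failure across the trial. The support is thin. Protocol section 9 links the conflict only to remote monitoring, and Protocol Appendix D says "Allowed modifications due to COVID-19 and/or the geo-political conflict in Ukraine and surrounding impacted regions are detailed within the Operations Manual", a manual not among the documents reviewed. No affected sites are identified.

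**Conclusion.** The point holds for Period B. The MI rule reaches permanent COVID-19 stoppers without a justification that fits them, gives them close to on-drug response, and departs both from the estimand and from the SAP's treatment of other stoppers.

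The likely size is small: about 0.5 point per stopper in each arm relative to NRI, and about 2.5 points for three in APR/RZB alone. These figures assume imputed response equal to the planning rates. They are illustrations against NRI. They are not upper bounds, because a subject already clear can be imputed above the arm rate, and they do not measure bias against the truth. It would be tempting to say the rule always favours risankizumab, but the direction reverses if only apremilast subjects stop. Nothing here shows the planned sample size to be wrong: with 5% of both arms moved to NRI, Period B power is still 92.2%. The change is worth making because it is simple and no sensitivity analysis would otherwise expose the effect.

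**What to change.** For the Period B analyses, amend Appendix D 2.1 and 2.4, SAP 9.2.1 and the definition of the COVID19_XX flag. Use MI only when the missed visit is COVID-related and no permanent discontinuation of assigned study drug was recorded at or before the Week 44 visit. Week 44 is the last dosing visit shared by APR/RZB and APR/APR, so the condition applies equally to both. Otherwise apply the existing non-response rule, and keep using observed off-drug values. The ITT_LT comparison needs its own stated cut, since continuous risankizumab is last given at Week 40. Leave the Period A rule as it is.

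In the sample code, the NRI override writes dataset ALLF but PROC FREQ reads ALL. The flag takes effect only if the analysis reads the overridden data.

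Secondary: if missed visits caused by the conflict are documented as such in subjects still on drug, handle them under the same MI rule as COVID-19 logistical misses. This requires the reason to be captured; Protocol section 9 describes supplemental forms for COVID-19 only.

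Cost: SAP wording and one condition on an existing flag. A few COVID-19 stoppers become non-responders, so the reported difference may be slightly less favourable.

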2.2 Multiple Imputation (MI) and MAR Assumption

When a dichotomized variable is derived from a continuous scale, for example, PASI 90 (at least a 90% reduction in PASI relative to Baseline), the multiple imputation will be applied to the original scale, PASI (ranges from 0 – 72) assuming multivariate normal distribution. Then the dichotomized variable will be derived from the imputed value.

The MI procedure assumes that the data are missing at random (MAR). That is, for an outcome variable Y, the probability that an observation is missing depends only on the

observed values of other variables, not on the unobserved values of the outcome variable Y. Statistical inference from the MI procedure is valid under the MAR assumption.

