## Disease/Condition Activity

- ✓ 6. Male or female subject with a diagnosis of chronic plaque PsO with or without PsA, for at least 6 months prior to Baseline.
- ✓ 7. Stable moderate chronic plaque PsO at both Screening and Baseline as defined as:
  - BSA  $\geq 10\%$  and  $\leq 15\%$ ,
  - PASI  $\geq 12$ , and
  - sPGA = 3 (moderate) based on a 5-point scale (0 to 4).
- ✓ 8. PsO inadequately controlled disease by topicals, phototherapy and/or systemic treatments.
- ✓ 9. Subject must be a candidate for systemic therapy as assessed by the investigator.

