Repeat the imputation process $K=30$ times using the procedure described above to form $K=30$ monotone missing datasets, where K is determined as described in "Repetition of Imputations (K)."

Imputation Step

For missing data with monotone missing patterns, the choice of multiple imputation using a parametric regression model that assumes multivariate normality is appropriate.

The imputation step is described below:

- The imputation model for the missing data is a regression model, which controls for the same variables for each Population as listed in the augmentation step. The covariates included in the model and the order of these variables are consistent with the augmentation step.
- For each monotone missing dataset, using SAS PROC MI with MONOTONE REG model statement, the outcome variable at each post-baseline visit with missing values will be imputed sequentially with covariates constructed from their corresponding sets of preceding variables.

A 'complete' dataset with imputed values for the missing data is generated after the augmentation and imputation steps are completed.

Repetition of Imputations (K)

Repetition of imputations, K, must be determined in advance. When estimating the overall variance of multiple imputation, the additional sampling variance is the between-imputation variance divided by K. This value represents the sampling error associated with the overall or average coefficient estimates. It is used as a correction factor for using a specific number of imputations. The more imputations (K) are conducted, the more precise the parameter estimates will be. For example, with a 1% power falloff tolerance in multiple imputation, as compared to an infinite number of imputations, multiple imputation requires 20 repetitions of imputation for 30% missing information and 40 repetitions for 50% missing information (Graham, Olchowski, and Gilreath 2007⁴). In the usual clinical settings expecting less than 30% missing information, K=30 repetitions are deemed sufficient. When missingness exceeds 30%, depending on the power falloff tolerance level, number of repetitions may need to be increased. Recent research⁴ suggested that the number of repetitions (K) should be at least equal to the percentage of missing (White et al., 2011⁶)

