3.0 Sample SAS Code

```

/*****/
/*IMPUTATION ALGORITHM*/
/*****/
/*NOTE: THIS APPROACH REQUIRES NO MISSING IN CATEGORICAL COVARIATES AND
REQUIRES AT LEAST ONE OBSERVATION IN BASELINE OR ONE OF THE POST-
BASELINE VISIT*/
/*PASI 90 at Week 16 is used as an example in the sample code*/

/*PRE-AUGMENTATION - CREATE DUMMY FOR CATEGORICAL VARIABLES*/
/*****/
DATA PASI_2; SET PASI;
  /*THE MCMC STATEMENT BELOW ASSUMES MULTI-VARIATE NORMAL*/
  IF TRT01PN=1 THEN TRT1=1; ELSE TRT1=0;
  /*BASELINE WEIGHT AND PRIOR BIO/SYS CATEGORY*/
  IF PSOBLGN = 1 THEN REG1 = 1 ;ELSE REG1 = 0;
RUN;

/*AUGMENTATION STEP -- TO HAVE 30 MONOTONE MISSING DATASETS*/
PROC MI DATA= PASI 2 OUT= PASI MONO NIMPUTE=30 SEED= 12345 /*ACTUAL
RANDOM SEED PRE-DEFINED AS THE NUMERICAL VALUE OF THE DATE OF FIRST
SUBJECT FIRST DOSE*/
  ROUND=. . . 0.1 0.1 0.1 /*VALUE ROUND TO 1ST DECIMAL*/
  MIN=. . . 0 0 0 /*MINIMUM VALUE OF PASI IS 0*/
  MAX=. . . 72 72 72 /*MAXIMUM VALUE OF PASI IS 72*/
MCMC IMPUTE=MONOTONE ;
/*NOTE: CATEGORICAL VARIABLES SUCH AS TRT1 TRT2 ARE DUMMY, CREATED
ABOVE*/
/*NOTE: ALL OTHER NON-DUMMIED COVARIATES MUST BE CONTINUOUS*/
/*SUPPOSE STRATAN (NUMERIC VARIABLE FOR STRATA) HAS ONLY 2 LEVELS, NO
NEED TO CREATE DUMMY*/
VAR TRT1 REG1 WTBL BASE WK4 WK16;
/*CAUTION TO USE THE "BY" STATEMENT IN MCMC: */
/*MVN MODEL IS FITTED WITHIN EACH 'BY' GROUP, INSTEAD OF ACROSS ALL
GROUPS*/
RUN;

/*IMPUTATION STEP - DETERMINE IMPUTATION DISTRIBUTION AND RANDOMLY
IMPUTE MISSING VALUE TO GENERATE 'COMPLETE' DATASETS*/
/*****/
```

```
PROC MI DATA= PASI MONO OUT= PASI FULL NIMPUTE=1 SEED= 54321 /*ACTUAL
RANDOM SEED PRE-DEFINED AS THE NUMERICAL VALUE OF THE DATE OF LAST
SUBJECT FIRST DOSE */
  ROUND= . . . 0.1 0.1 0.1 /*VALUE ROUND TO 1ST DECIMAL*/
  MIN=. . . 0 0 0 /*MINIMUM VALUE OF PASI IS 0*/
  MAX=. . . 72 72 72 /*MAXIMUM VALUE OF PASI IS 72*/
  MINMAXITER=1000;
  /*CLASS CATEGORICAL VARIABLES TRT1 AND REG2*/
  CLASS TRT1 REG1;
  VAR TRT1 REG1 WTBL BASE WK4 WK16;
  MONOTONE REG (WK4 WK16); /* IMPUTED SEQUENTIALLY, FROM WK 4 TO 16,
WITH COVARIATES CONSTRUCTED FROM THE CORRESPONDING PRECEDING VARIABLES*/
  BY IMPUTATION ; /*FOR EACH OF THE 30 MONOTONE
MISSING DATASETS, IMPUTE A 'COMPLETE' DATASET*/
RUN;

/*DETERMINE DICHOTOMOUS RESPONSE STATUS, PASI 90 AT WEEK 16*/
DATA ALL; SET PASI FULL;
  IF 0<=WK16<=0.1*BASE THEN PASI90_16=1;
  ELSE PASI90_16=0;
RUN;

/*****
*/
/*          DATA HANDLING STEPS TO MERGE COVID-19 STATUS OMITTED
*/
/*          PLACE TO ADD DATA HANDLING AND MERGING STEPS
*/

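### Imputing COVID-missing PASI from a zero-bounded normal model and then dichotomising under-counts PASI 90 responders: under stated assumptions, to about 0.4–0.6 of the true risankizumab rate at Week 16

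*SAP*

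**What the plan says.** SAP 9.2.1 and Appendix D count missing responses as failures, with two exceptions: a visit flanked by responses on both sides, and data missing because of COVID-19, which are multiply imputed.

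Appendix D 2.2 sets the rule for the second exception. "When a dichotomized variable is derived from a continuous scale", with PASI 90 as the example, the raw score is imputed "assuming multivariate normal distribution. Then the dichotomized variable will be derived from the imputed value". Appendix D 2.3 states that "the choice of multiple imputation using a parametric regression model that assumes multivariate normality is appropriate". The sample code (Appendix D 3.0) implements this with MONOTONE REG on "VAR TRT1 REG1 WTBL BASE WK4 WK16". Treatment is only a covariate there, so both arms share one residual variance. The code sets a lower bound ("MINIMUM VALUE OF PASI IS 0") and an upper bound of 72, rounds to 0.1, and calls a subject a PASI 90 responder when Week 16 PASI is between 0 and 0.1 × Baseline.

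SAP 9.2 says that sensitivity analyses will assess the effect of missing data. Sections 9.3.3 and 9.4.3 then plan none for the primary and ranked secondary endpoints.

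**The concern.** Entry requires PASI of at least 12 (Protocol 5.1, criterion 7), so the responder cut is only 1.2 for a Baseline of 12 and 1.8 for a Baseline of 18. Protocol 2.2 says that most risankizumab subjects in psoriasis studies reached 90% improvement, so most observed risankizumab values should lie in that narrow band next to 0. A normal error whose spread is shared with the more variable apremilast arm, and whose negative draws are redrawn, spreads imputed values well above the cut.

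The missing-at-random argument in Appendix D does not protect against this, because it concerns why data are missing and not the shape of the imputation model. A larger number of imputations does not help either.

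What is at stake is the estimated difference in response percentages (SAP Tables 1 and 2) and the purpose of the imputation, which is to avoid treating COVID-missing subjects as failures.

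**Working it through.** **1. The plan's own figures.** Power = Φ[(|p1 − p2| − 1.96·SE0)/SE1], with SE0 pooled and SE1 unpooled. For Period B (60 per group, 50% vs 20%; SAP 2.4):
- SE0 = √(0.35 × 0.65 × 2/60) = 0.0871
- SE1 = √((0.25 + 0.16)/60) = 0.0827
- Power = Φ[(0.30 − 0.1707)/0.0827] = Φ(1.56) = 94%

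This agrees with the stated figure of more than 90%. For Period A (110 vs 220, 40-point difference) power exceeds 99.9% for apremilast rates of 5% to 30%.

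**2. Closed form.** For cut c, predicted mean m and residual SD s, the imputed response probability is [Φ((c − m)/s) − Φ(−m/s)] / [1 − Φ(−m/s)]. Assume Baseline PASI 15, so c = 1.5, and s from 2.0 to 3.2. The documents give neither.

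| Predicted PASI | s = 2.0 | s = 3.2 |
|---|---|---|
| 0 | 0.55 | 0.36 |
| 1.5 (on the cut) | 0.35 | 0.27 |
| 2 | 0.29 | 0.23 |

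A subject predicted to be completely clear is imputed as a responder only 36–55% of the time.

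**3. Simulation of the SAP algorithm at Week 16.** Assumptions:
- 110 vs 220 subjects, Baseline PASI 12 plus a gamma variate with mean 3
- a skewed (beta) fraction of Baseline PASI remaining
- 10% of Week 16 values missing at random, Week 4 observed

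Risankizumab PASI 90 among the missing:

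| Assumed RZB / APR PASI 90, correlation | Residual SD | True | Normal (SAP) | Matching | Logistic | Normal/true |
|---|---|---|---|---|---|---|
| 0.55 / 0.15, 0.6 | 2.58 | 0.530 | 0.282 | 0.538 | 0.545 | 0.53 |
| 0.65 / 0.10, 0.6 | 2.88 | 0.657 | 0.293 | 0.631 | 0.644 | 0.45 |
| 0.75 / 0.10, 0.3 | 2.82 | 0.760 | 0.296 | 0.726 | 0.743 | 0.39 |

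The normal method returns about 0.29 whether the truth is 53% or 76%. Over a wider grid (risankizumab PASI 90 0.50–0.75, apremilast 0.05–0.20, correlation 0.3–0.8; residual SD 2.0–3.2) the ratio was 0.38–0.60. A separate simulation gave 0.24–0.32 against true rates of 0.49–0.78, and matching done by arm recovered 0.48–0.77. Apremilast PASI 90 is also under-imputed, at roughly 0.4–0.95 of its true rate.

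**4. Week 52.** With earlier Period B visits observed, the risankizumab ratio was 0.45–0.64 at visit correlations of 0.5–0.7 and 0.71–0.87 at 0.9–0.95.

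**5. Effect on the difference.** With missing fraction f and ratios kR and kA, the loss is f × [pR(1 − kR) − pA(1 − kA)].
- **Period A, f = 5%, assumed 60% vs 20%.** With kR = 0.4 and kA = 0.6, the loss is 0.05 × (0.36 − 0.08) = 1.4 points. With kR = 0.6 it is 0.05 × (0.24 − 0.08) = 0.8 points. Other assumed rates gave 1.4 points (55% vs 15%) and 1.9 points (65% vs 15%, a 50-point difference). Plain non-responder imputation would lose 0.05 × 40 = 2.0 points.
- **Period B, f = 10%, 50% vs 20%, kA = 0.6.** With kR = 0.5, the rates become 0.475 and 0.192, a difference of 28.3 points with power 92%. With kR = 1/3, they become 0.467 and 0.192, a difference of 27.5 points with power 90%. At f = 20% the same ratios give power of 89% and 85%.
- **Period B, high visit correlation, f = 10%.** With kR = 0.87 and kA = 0.85, the loss is 0.10 × (0.065 − 0.03) = 0.35 points and power stays near 94%.

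**The case against.** Most of the case against limits the size of the problem, and it stands. Only COVID-missing records are affected. The bias runs toward no difference, so it cannot manufacture superiority. The method also remains less biased than plain non-responder imputation.

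Every size above rests on assumed inputs. A reader might infer that imputed response falls to a third or less of truth. The documents do not support that. In these simulations such a ratio (0.30) appeared only when apremilast PASI was allowed to rise to 150% of Baseline, giving a residual SD of about 4.5, with a true risankizumab rate of about 0.77. The same worsening with a true rate of about 0.57 gave 0.38.

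A reader might also infer that sPGA 0/1 is imputed by the same normal model. Appendix D 2.2 covers variables derived from a continuous scale, and its example and code are PASI only. The sPGA model is simply not stated. If sPGA were imputed that way and rounded to whole grades, the simulated shortfall would be modest (ratio about 0.85–0.90).

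Raw-scale imputation also has a real merit: it keeps PASI 75, 90 and 100 consistent within a subject. The remedy should preserve that.

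None of this removes the mechanism, which follows from the stated rule and appeared under every skewed distribution tried.

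**Conclusion.** The point holds as a bias of estimation. Under the assumptions above, Appendix D imputes COVID-missing risankizumab subjects as PASI 90 responders at about 0.4–0.6 of their true rate at Week 16 and 0.45–0.87 at Week 52.

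In Period A this costs about 1–2 points at 5% missing, and the test decision is not at risk. In Period B it costs up to about 2–2.5 points at 10% missing, with power falling from 94% to about 90–92%. Those Period B figures use risankizumab ratios of one third to one half, at or below the low end of the Week 52 range. PASI is also recorded at Week 44, so a higher correlation with Week 52, and a smaller loss, is plausible.

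It would be wrong to conclude that type I error is inflated or that the trial's main conclusion is threatened. The change is still worth making: it is cheap, the reported difference is biased without it, and no planned analysis of the primary or ranked endpoints would show the problem.

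**What to change.** In Appendix D 2.2–2.3 and the sample code, replace MONOTONE REG with predictive mean matching on raw PASI, run separately by arm. Imputed values are then observed PASI scores from the same arm, earlier PASI scores stay in as predictors, and PASI 75, 90 and 100 remain consistent. Week 16 and Week 52 are the last visits of their periods, so the primary and ranked endpoints are always filled in this step and not in the normal augmentation step before it.

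Logistic imputation of the binary response is a secondary option. It removed most of the bias in simulation, but imputing each response separately can make a subject a PASI 90 responder and a PASI 75 non-responder.

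For sPGA 0/1, state the model: logistic or ordinal, without Baseline sPGA, which is 3 for every eligible subject and so carries no information. Reconcile SAP 9.2 with 9.3.3 and 9.4.3 on sensitivity analyses.

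The cost is SAP wording, a changed PROC MI statement, and a limited donor pool in the smaller arms (110 risankizumab subjects in Period A, about 60 per group in Period B).
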